14.5 TREATMENT RANDOMIZATION AND BLINDING

There is no randomization for this study.

14.6 ANALYSIS POPULATIONS

The safety population will consist of all subjects receiving at least 1 dose of study medication. All subjects who received at least one dose of study treatment and had at least 1 post-baseline response evaluation will be included in the efficacy analysis set. Following completion of the study, best response will be determined for each subject in accordance with RECIST v.1.1 guidelines and the objective response rate presented for each dose cohort.

14.6.1 Patient Disposition

The number and percent of patients entering and completing the clinical study will be presented by dose and cohort and study Part.

14.6.2 Demographic Information and Baseline Characteristics

Demographic and baseline characteristic will be descriptively summarized by study phase and dose treatment.

14.7 PROTOCOL DEVIATION

Protocol deviation will be listed by patient

14.8 INTERIM ANALYSIS

No formal interim analysis is planned for the study. However, reports will be generated post the dose escalation part 1 of the study and adverse events and toxicity reports will be monitored.

14.9 HANDLING OF MISSING DATA

The data for the efficacy endpoint will be analyzed as Intention to treat (ITT) and according to protocol (ATP). Primary endpoint estimate and associated hypothesis testing will be provided for both ITT and ATP analyses. The OS rate as a secondary endpoint analysis will be provided for ITT and ATP.

16.0 APPENDIX A

APPENDIX A

Performance Status Criteria

ECOG Performance Status Scale		Karnofsky Performance Scale	
Grade	Descriptions	Percent	Description
0	Normal activity. Fully active, able to carry on all pre-disease performance without restriction.	100	Normal, no complaints, no evidence of disease.
		90	Able to carry on normal activity; minor signs or symptoms of disease.
1	Symptoms, but ambulatory. Restricted in physically strenuous activity, but ambulatory and able to carry out work of a light or sedentary nature (e.g., light housework, office work).	80	Normal activity with effort; some signs or symptoms of disease.
		70	Cares for self, unable to carry on normal activity or to do active work.
2	In bed <50% of the time. Ambulatory and capable of all self-care, but unable to carry out any work activities. Up and about more than 50% of waking hours.	60	Requires occasional assistance, but is able to care for most of his/her needs.
		50	Requires considerable assistance and frequent medical care.
3	In bed >50% of the time. Capable of only limited self-care, confined to bed or chair more than 50% of waking hours.	40	Disabled, requires special care and assistance.
		30	Severely disabled, hospitalization indicated. Death not imminent.
4	100% bedridden. Completely disabled. Cannot carry on any self-care. Totally confined to bed or chair.	20	Very sick, hospitalization indicated. Death not imminent.
		10	Moribund, fatal processes progressing rapidly.
5	Dead.	0	Dead.

17.0 APPENDIX B: HCCC CLINICAL TRIAL DATA AND SAFETY MONITORING PLAN (DSMP)*

Date: 03/12/2019

IRB#: 201507716

IND#: Exempt #126767

Title: A Therapeutic Trial for Safety and Preliminary Efficacy of the Combination of Axitinib and Selenomethionine (SLM) for Adult Patients with Advanced Metastatic Clear Cell Renal Cell Carcinoma (CCRCC)

PI: [name]

* *All investigator-initiated protocols will be subject to ongoing monitoring of accrual, subject eligibility, protocol modifications and continuing reviews. Active studies will be audited for the DSMC by the CRSO, following guidelines based on level of risk to subjects. Audits will be conducted by reviewing subject files provided by clinical research coordinators, as well as original source documentation provided by online medical records and research pharmacists. The CRSO will review adverse events, eligibility of subjects, and adherence to the IRB- and PRMC-approved protocol. Protocols found to have discrepancies will be require a response from the PI and an action plan for correcting identified deficiencies. The DSMC will provide a schedule of audit and report dates if requested.*

Type of Clinical Trial:

- Investigator-initiated (UI/HCCC)
- Pilot study
- Phase I/II
- Phase III
- Interventional Treatment
- Non-Interventional
- Investigator-initiated, participating site
- Phase I
- Phase II
- Compassionate-use/Expanded Access
- Interventional Non-Treatment

Study risk-level:

- Level 1—low risk of morbidity or death, * <1% of death or any adverse event
- Level 2—risk of death* <1% or any adverse event 1% – 5%
- Level 3—risk of death* 1% – 5% or grade 4 – 5 SAE 1% – 5%
- Level 4—risk of death* >5% or grade 4 – 5 SAE >5%
- Drugs being used on a “compassionate” basis

* *Risk of death* refers specifically to 100-day treatment-related mortality

Reporting and Monitoring Requirements:

All institutional investigator initiated trials (IITs), regardless of assigned risk level are subject to routine DSMC monitoring activities which may include but are not limited to review of signed consent documents, eligibility and adverse event reporting.

All institutional IITs have the following **reporting requirements** as part of their DSMP:

- Register all subjects in HCCC's Clinical Trial Management System, OnCore
- Document Adverse Events
- Document protocol deviations
- Provide an annual progress report to the DSMC via OnCore data export

Selected monitoring strategy based on risk-level:

Risk Level 4

Interventional treatment trials involving investigational agents or devices with a risk of death* (>5% or grade 4 – 5 SAE >5%), e.g. all investigator initiated INDs, most Phase I/II trials, gene therapy, gene manipulation or viral vector systems high-risk clinical procedures if performed solely for research purposes. The use of a new chemical or drug for which there is limited or no available safety data in humans.

Study Safety Review

An independent study monitor and/or the DSMC Chair (or designee), will review study data (provided by the PI/available in OnCore) and communicate with the PI at least biannually. A copy of this communication will be forwarded to the DSMC and PRMC Chairs.

Additional Reporting Requirements:

- A scanned copy of the completed eligibility checklist, with screening information and PI signature, will be attached in OnCore for ongoing review by DSMC staff.
- Serious adverse events will be entered directly into an OnCore SAE report by the research team. OnCore will send an automatic notification to the DSMC Chair/acting Chair and staff for review.
- The DSMC utilizes a risk-based monitoring approach. The trial's research records will be monitored at minimum twice per year. Monitoring may be done more frequently depending on the protocol, risks to subjects, reported serious/adverse events, patient population and accrual rate. Records for a minimum of 25% of subjects will be monitored for the entire study.

Monitoring will involve the following:

- review eligibility of patients accrued to the study,
- check for the presence of a signed informed consent,
- determine compliance with protocol's study plan,
- determine whether SAEs are being appropriately reported to internal and external regulatory agencies,
- compare accuracy of data in the research record with the primary source documents,
- review investigational drug processing and documentation,
- assess cumulative AE/SAE reports for trends and compare to study stopping rules.

Routine Adverse Event Reporting

For non-serious Adverse Events, documentation must begin from the first day of study treatment and continues through the 30 day follow-up period after the last dose of the investigational agent.

Collected information should be recorded in the electronic/Case Report Forms (eCRF/CRF) for that subject. A description of the event, its severity or toxicity grade (according to [NCI's Common Toxicity Criteria \(CTCAE\)](#)), onset and resolved dates (if applicable), and the relationship to the study drug should be included. Documentation should occur in real time. The principal investigator has final responsibility for determining the attribution of the event as it is related to the study drug.

Serious Adverse Event Reporting

For any experience or condition that meets the definition of a serious adverse event (SAE), recording of the event must begin after signing of the informed consent and continue through the 30 day follow-up period after treatment is discontinued.

Investigators must report to the DSMC any serious adverse events (SAE), whether or not they are considered related to the investigational agent(s)/intervention (21 CFR 312.64). SAEs must be reported via an OnCore SAE Report within 24 hours of learning of the event.

An adverse event is considered **serious** if it results in ANY of the following outcomes:

1. Death
2. A life-threatening adverse event
3. An adverse event that results in inpatient hospitalization OR prolongation of existing hospitalization for ≥ 24 hours
4. A persistent or significant incapacity or substantial disruption of the ability to conduct normal life functions
5. A congenital anomaly/birth defect.
6. Important Medical Events (IME) that may not result in death, be life threatening, or require hospitalization may be considered serious when, based upon medical judgment, they may jeopardize the patient or subject and may require medical or surgical intervention to prevent one of the outcomes listed in this definition. (FDA, [21 CFR 312.32](#); [ICH E2A](#) and [ICH E6](#)).

FDA Reporting Requirements (for Sponsor-Investigators)

It is the responsibility of the IND sponsor-investigator to comply with IND safety reporting as set forth in the Code of Federal Regulations, [Section 312.32](#). This responsibility includes providing an annual IND report to the FDA.

All IND safety reports must be submitted on [Form 3500A](#) and be accompanied by [Form 1571](#). The type of report (initial or follow-up) should be checked in the respective boxes on Forms 3500A and 1571. See [Instructions for](#)

[completing Form 3500A.](#) Please note all instance of UIHC, location, and faculty / staff should be redacted from supporting documentation and the 3500A.

The submission must be identified as:

- “IND safety report” for 15-day reports, or
- “7-day IND safety report” for unexpected fatal or life-threatening suspected adverse reaction reports, or
- “Follow-up IND safety report” for follow-up information.

For detailed explanation of the above definitions, requirements, and procedures related to IND application safety reports and the responsibilities of IND applications sponsors with regard to such reporting, refer to [Guidance for Industry and Investigators: Safety Reporting Requirements for INDs and BA/BE Studies \(PDF - 227KB\)](#)

In addition to completing appropriate patient demographic and suspect medication information, the report should include the following information within the Event Description (section 5) of the MedWatch 3500A form:

- Treatment regimen (dosing frequency, combination therapy)
- Protocol description (and number, if assigned)
- Description of event, severity, treatment, and outcome, if known (grading the event per CTCAE)
- Supportive laboratory results and diagnostics
- Sponsor-Investigator’s assessment of the relationship of the adverse event to each investigational product and suspect medication

Data Monitoring and Management

Subject Registration

All studies that undergo PRMC review and/or utilize HCCC Clinical Research Services (CRS) resources are required to register subjects in OnCore. Each subject registration includes the following:

- The subject’s IRB approved (version date) consent form and the date of their consent
- Date of eligibility and eligibility status (eligible, not eligible)
- On study date and subject’s disease site (and histology if applicable)
- On treatment date (if applicable)

All subject registration information is expected to be entered into OnCore within **2 (two) business days** after the subject’s study visit.

Subject Data

For HCCC investigator initiated trials, research staff are responsible for entering subject study data (data collection) into OnCore electronic case report forms (eCRFs). These eCRFs must be approved by the PI and statistician prior to study activation to ensure sufficient and necessary data acquisition. All information entered into eCRFs will be traceable to the source documents which are generally maintained in the subject’s file.

eCRF data entry needs to be timely and should be entered into OnCore as soon as possible but no later than **14 (fourteen) business days** after the subject's visit, including adverse events, tumor measurements, administration of study medication, concomitant medications, labs, and vitals. Physical exam assessments must be entered no later than **14 (fourteen) business days** following completion of the physician's clinic note in the medical record.

Timely data entry facilitates remote monitoring of data, allows the data to progress appropriately through the data cleaning process, and helps prevent a backlog of data queries.

Forms Monitoring

OnCore eCRF data are monitored on a routine basis (dependent on accrual) to ensure all data are entered completely, accurately, and within time requirements outlined above. The assigned DSMC monitor will coordinate and complete the data monitoring review. When the time comes to monitor a study (based on patient accrual and assigned risk level of trial) the monitor arranges for a selection of cases to be reviewed from among the subjects registered in OnCore. As part of the forms monitoring process, the assigned monitor will issue queries via OnCore (linked to the eCRF) to resolve missing, incomplete, and/or incorrect information. A member of the research team is expected to respond to these monitoring queries within **14 (fourteen) business days**.

The monitoring process can often identify misunderstandings or deficiencies in the written, research protocol requirements earlier in the study process and thereby improve data quality and reduce rework.

Final Reports

A summary of each subject's data record is continually available to the PI, research staff, and DSMC from OnCore's Biostat Console. The availability of this information is a valuable tool for the preparation of final reports and manuscripts as well as ongoing deficiency reports.

18.0 APPENDIX C: SLM RUN-IN PHASE

Subject Initials: _____

Cycle Start Date: _____ / _____ / _____

INSTRUCTIONS TO THE PATIENT:

You will take one Selenium (SLM) capsule _____ mcg twice a day for 14 days.

Record the date and time (HH:MM) you took study your medication in the space provided below.

If you have any comments or notice any side effects, please record them in the Comment column.

Please bring your medication bottles and this diary with you at each visit to review with the study team.

If you have any questions or concerns, please call your study nurse **[name] [contact]** (usual business hours M-F).

After hours and weekends, please call the hospital operator at [contact] and ask for the cancer doctor on-call.

Date	Day	SLM AM Dose time	SLM PM Dose time	Axitinib AM Dose time	Axitinib PM Dose time	Comments
	1					
	2					
	3					
	4					
	5					
	6					
	7					
	8					
	9					
	10					
	11					
	12					
	13					
	14					

PATIENT DRUG DIARY, Cycle 1 and beyond

Subject Initials: _____

Cycle Start Date: ____ / ____ / ____

Cycle: ____

INSTRUCTIONS TO THE PATIENT:Dose: Selenium (SLM) _____ mcg **once** daily, and Axitinib (Inlyta) _____ mg **twice** daily.

Record the date and time (HH:MM) you took study your medication in the space provided below.

If you have any comments or notice any side effects, please record them in the Comment column.

Please bring your medication bottles and this diary with you at each visit to review with the study team.

If you have any questions or concerns, please call your study nurse **[name] [contact]** (usual business hours M-F).

After hours and weekends, please call the hospital operator at [contact] and ask for the cancer doctor on-call.

Date	Day	SLM AM Dose time	Axitinib AM Dose time	Axitinib PM Dose time	Comments
	1				
	2				
	3				
	4				
	5				
	6				
	7				
	8				
	9				
	10				
	11				
	12				
	13				
	14				
	15				
	16				
	17				
	18				
	19				
	20				
	21				
	22				
	23				
	24				
	25				
	26				
	27				
	28				

- The EDTA 2 ml tube drawn for visit is not to be spun and taken to campus mail before 1330 to be shipped.

Revised 3/20/17

20.0 SLM STUDY LAB CALENDAR ESCALATION SUBJECTS (BASED ON V9 PROTOCOL)

Test	Day 1	Day 14 (Cycle 1)	C2 (Day 1)	C3	C4	C5	C6	C7	C10	C13
SLM (3 ml purple tube)	Pre & Post 2 Hours	Pre & Post 2 Hours	Pre & Post 2 Hours	Post 2 Hours	Post 2 Hours	Pre & Post 2 Hours	Post 2 Hours	Pre & Post 2 Hours	Post 2 Hours	Post 2 Hours
miRNA (6ml purple tube)	Pre	Pre								
Biomarkers (6 ml pink tube)	Pre	Pre	Post 2 Hours	Post 2 Hours	Post 2 Hours	Post 2 Hours	Post 2 Hours	Post 2 Hours	Post 2 Hours	

20.1 SLM STUDY LAB CALENDAR EXPANSION SUBJECTS

Test	D1	D14	C2	C3	C4	C7	C10
SLM (3 ML purple tube)	Pre and 2 hour post	2 hr post only					
miRNA (6 ml purple tube)	Pre	2 hr post only					
Biomarkers (6 ml pink tube)	Pre	2 hr post only					

20.2 20.2 SLM STUDY LAB CALENDAR PILOT SUBJECTS

Test	D1	D14	C2	C3	C4	C7	C10	C13
SLM (3 ML purple tube)	Pre	2 hr post only	X	X	X	X	X	X
miRNA (6 ml purple tube)	Pre	2 hr post only						
Biomarkers (6 ml pink tube)	Pre	2 hr post only	X	X	X	X	X	X

21.0 DUAL ENERGY CT PROTOCOL

21.1 OBJECTIVE

From [name]: *The current plan is to do CT (your protocol) at baseline, day 14 (+/- 2 days) and at 2 months after SLM axitinib. All these 3 series will be done using your protocol. Dual Energy CT's will be covered by research money (day 14 scan does NOT need to be interpreted by [name]).*

21.2 CT PROTOCOL

The same CT scan protocol will be obtained at 3 time points;

- Visit 1: baseline prior to treatment
- Visit 2: 14 ± 2 days following start of SLM
- Visit 3: 56 ± 3 days following start of chemotherapy (axitinib)

If for any reason baseline DECT could not be performed, we will utilize only regular CT scan subsequently in that setting (cancel further DECT) and there will NOT be a need for day 14 scan. This need to be discussed by PI before enrollment on study.

21.3 DUAL ENERGY CT:

- Contrast: 50% saline mixed with 50% 370mg/ml Iopamidol delivered at 4ml/s (4ml/s (35 s+ 5s) = 160ml of which 80ml is contrast) with delay of 35s (for chest) and 70s (for abdomen/pelvis)
- Positioning: Cranialcaudal acquisition with scan coverage (DFOV) from pubic symphysis to apex of lungs (DFOV to match prior visit). Acquisition at coached total lung capacity (TLC) (recorded for DECT)
- Acquisition: CHEST: The spiral DECT contrast scan with dose modulation with tube A: 120 ref mAs/80kV, tube B: 67 ref mAs/Sn150 kV, with a pitch of 0.55 and rotation time of 0.25sec. The CTDIvol is assumed to be 4.28mGy, with total DLP of 143.2mGy*cm for a 30cm scan.
- Acquisition: ABDOMEN: The spiral dual energy contrast abdomen/pelvis scan protocol uses dose modulation with tube A: 190 ref mAs/100kV, tube B: 95 ref mAs/Sn150 kV, with a pitch of 0.55 and rotation time of 0.25sec. The CTDIvol is assumed to be 10.41mGy, with total DLP of 553.7mGy*cm for a 50cm scan.
- Reconstruction: R1: 0.75 x0.5; R2: 2.0 x 1.4, Qr40(Admire 5), FOV to match prior visits, Energy Series: A, B and M. Keep Raw data.

21.4 ANALYSIS

- Hypothesis: SLM will improve vascularization of tumors (ie increase in tumor iodine density at visit 2) which will allow for more effective chemotherapy treatment (ie decrease in tumor iodine density at visit 3, and decrease in tumor size). Secondary analysis may examine if baseline (visit 1) levels correlate with SLM response and/or treatment outcome (ie tumors with poor vascularization at visit 1, benefit more from SLM).

- Syngo via (initial analysis on 2.0x 1.4 recon) to produce virtual non-contrast image (VNC), mono energetic 40keV, Iodine concentration PBV (HU and mg/ml)
- Examine analysis results using fixed region of interest (ROI) in tumor volume vs semi-automatic tumor segmentation.

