2.5 AXITINIB AS A SECOND LINE THERAPY IN METASTATIC CCRCC

Axitinib is an oral, potent, and selective inhibitor of VEGF receptors 1, 2, and 3. In a phase II study, axitinib was found active in cytokine-refractory metastatic renal cell cancer (Rixe). Responses were reported with the use of chemotherapy, hormone or biological treatment. The objective response rate was 44·2% for patients treated with axitinib. In a phase III trial comparing axitinib to sorafenib as second line treatment for advanced CCRCC, PFS was 6.7 months in the axitinib arm and 4.7 months in the sorafenib arm ($p<0.0001$), with manageable toxicities (Rini, lancet). Thus CCRCC offers an excellent opportunity for proof of concept, in a relatively small sample size, that sustained inhibition of HIF- α and VEGF by the sequential and concurrent combination of SLM and axitinib is safe and could possibly impact significantly on treatment outcome.

Approach to treatment of clear cell renal cell carcinoma

Setting		First choice	Alternative
First-line therapy	0 to ≤ 2 risk factors	HD IL-2	Sunitinib
			Bevacizumab plus IFN-alfa
			Pazopanib
	>2 risk factors	Temsirolimus	Sunitinib
Second-line therapy	Prior cytokine	Axitinib	Pazopanib
			Sunitinib
		Sorafenib	Temsirolimus
	Prior VEGFR inhibitor		Bevacizumab
		Everolimus	Clinical trials
		Axitinib	
		Sorafenib	
	Prior mTOR inhibitor	Clinical trials	

Risk factors: poor Karnofsky Performance Status, serum lactic dehydrogenase (LDH) level >1.5 times the upper limit of normal, corrected serum calcium >10 mg/dL (2.5 mmol/L), hemoglobin concentration less than the lower limit of normal, and absence of nephrectomy (ie, no disease-free interval).

HD IL-2: high-dose interleukin 2; IFN-alfa: interferon alfa; mTOR: mammalian target of rapamycin; VEGFR: vascular endothelial growth factor receptors.

Courtesy of [name].

UpToDate®

[figure not shown]

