5.3 SLM AND AXITINIB ADMINISTRATION

SLM oral capsules will be given twice daily alone for the first 14 days, then once daily in combination with Axitinib thereafter. SLM dosing will be based on patient BSA for the Pilot phase and tolerance based on DLT assessments during run-in only. See section 14.4 for dosing information for the Pilot portion. SLM will be provided by the study free of charge, by Sabisna Corporation located in NJ, USA. SLM will be stored in the Investigational Pharmacy at University of Iowa Hospitals and Clinics.

Axitinib oral tablets will be provided by the study free of charge from Pfizer and stored in the Investigational Pharmacy at the University of Iowa Hospitals and Clinics. Dosing will start at 5 mg twice daily, with the two doses taken 12 hours apart, with or without food. Axitinib will begin after the patient completes the 14 day SLM run-in portion of the trial.

Over the course of treatment, patients who tolerate Axitinib for at least two consecutive weeks with no adverse reactions >Grade 2 (according to the Common Toxicity Criteria for Adverse Events [CTCAE]) may have their dose increased as follows.

When a dose increase from 5 mg twice daily is recommended, the Axitinib dose may be increased to 7 mg twice daily, and further to 10 mg twice daily using the same criteria.

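### Section 21.4 takes a fall in tumor iodine and size at visit 3 as showing that SLM made treatment more effective, but with no axitinib-only comparator this link cannot separate SLM helping axitinib from axitinib working

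*Combined protocol and SAP*

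**What the plan says.** Section 21.4 states a chain of two links. The first is that "SLM will improve vascularization of tumors (ie increase in tumor iodine density at visit 2"). The second follows from it: "which will allow for more effective chemotherapy treatment (ie decrease in tumor iodine density at visit 3, and decrease in tumor size"). No reference visit, size of fall, test or comparator is given for the second link.

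The timing is in section 21.2: "Visit 2: 14 ± 2 days following start of SLM" and "Visit 3: 56 ± 3 days following start of chemotherapy (axitinib"). Section 5.3 adds that "Axitinib will begin after the patient completes the 14 day SLM run-in portion of the trial", and that SLM then continues once daily alongside axitinib. Section 14.5 says "There is no randomization for this study".

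Section 2.5 describes the partner drug: "Axitinib is an oral, potent, and selective inhibitor of VEGF receptors 1, 2, and 3". For a phase II study in cytokine-refractory disease it reports: "The objective response rate was 44·2% for patients treated with axitinib".

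The only other analysis of this kind in 21.4 is optional. It would correlate the baseline (visit 1) level with SLM response or with outcome.

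**The concern.** To say that treatment became more effective is to make a comparison with treatment without SLM. Section 21.4 replaces that comparison with a fall from an earlier scan in patients who all receive both drugs. Axitinib is an active antiangiogenic agent, and the section builds on a published dual-energy CT study of response to antiangiogenic treatment in this disease. A fall in iodine and in size is the direction axitinib alone would be expected to produce.

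The idea that SLM sensitizes tumors to axitinib is the trial's central hypothesis (section 2.7). If visit 2 iodine rises and the tumors then shrink, a report following 21.4 would present the whole mechanism as supported, even if SLM had added nothing to axitinib. No other planned analysis links the visit 2 change to later benefit.

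**Working it through.** The plan gives no sample size, power, threshold or error rate for dual-energy CT, so there is no figure to reproduce. The argument is one of design logic; the numbers only illustrate its scale.

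**Step 1. What each truth would look like, if axitinib works.**

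| Truth | Visit 2 iodine | Visit 3 iodine and size | Chain in 21.4 |
|---|---|---|---|
| SLM does nothing | no rise | fall | fails at the first link |
| SLM raises iodine, adds nothing to axitinib | rise | fall | counted as supported, wrongly |
| SLM raises iodine and helps axitinib | rise | larger fall | counted as supported, rightly |

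The last two rows differ only in the size of the fall, and the plan names no axitinib-alone value to set it against.

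**Step 2. Tumor size, with no SLM benefit.** Take the 44.2% response rate of section 2.5 and the 19 expansion patients, and assume that responses are reached by visit 3. Expected falls of at least 30%: 19 × 0.442 = 8.4. The binomial probability of at least 5 of 19 is 0.967.

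Now assume that percentage change is normal, with mean = −30 − SD × z(response rate), and apply a one-sided 5% t test against no change with n = 19:

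| Axitinib-alone response rate | SD 20 | SD 30 | SD 40 | SD 50 |
|---|---|---|---|---|
| 44.2% (z = −0.146) | 1.00 | 0.97 | 0.81 | 0.60 |
| 20%, assumed (z = −0.842) | 0.87 | 0.16 | 0.02 | below 0.01 |

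For example, at 44.2% and SD 20 the mean is −30 + 20 × 0.146 = −27.1%. At 20% and SD 40 it is +3.7%, so no average fall is expected. The fall is likely, not assured.

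**Step 3. Iodine, visit 3 link alone.** The documents give no iodine change on axitinib, so all inputs are assumed: a within-patient SD of log change of 0.3 to 0.5 and a between-patient SD of the axitinib effect of 0.2. Total SD = √(0.3² + 0.2²) = 0.36 to √(0.5² + 0.2²) = 0.54. The number scanned is 19 (expansion) to 29 (19 + 10 pilot). The mean log fall for a proportional fall f is −ln(1 − f), and the noncentrality is √n × mean / SD. Probability that a one-sided 5% paired t test is positive:

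| Axitinib-alone fall | Mean log fall | Positive |
|---|---|---|
| 10% | 0.105 | 21–46% |
| 20% | 0.223 | 54–95% |
| 30% | 0.357 | 87–100% |

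**Step 4. The whole chain if SLM does nothing.** Testing the visit 2 rise at one-sided 5% gives P(both links positive) ≤ P(visit 2 link positive) = 5%, whatever axitinib does later.

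**Step 5. Power of the replacement analysis.** For a true correlation of 0.5 at one-sided 5%, power = Φ(0.549 × √(n − 3) − 1.645).
- n = 29: Φ(2.80 − 1.645) = 0.88.
- n = 19: Φ(2.20 − 1.645) = 0.71.
- n = 15: Φ(1.90 − 1.645) = 0.60.
- n = 12: Φ(1.65 − 1.645) = 0.50.

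The smaller values are assumed but plausible. Section 21.6 requires eGFR above 45 for the scan, while section 3.1 admits creatinine clearance above 15. Under section 21.2 a missed baseline scan also cancels the later dual-energy scans.

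**Step 6. The outcome to avoid.** Visit 2 enters the visit 1 to visit 2 change with a plus sign and the visit 2 to visit 3 change with a minus sign. In the Step 3 model with no true link, their correlation is −w / (2√(w² + 0.2²)), where w is the within-patient SD. That is −0.42 at w = 0.3 and −0.46 at w = 0.5, in the direction the hypothesis predicts. Simulation of this model gave false support in 57–84% of trials.

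**The case against.** The strongest reply is that 21.4 states a chain, and its first link protects it. A reader might infer that the mechanism would be declared supported even if SLM did nothing. The documents do not support that: visit 2 is scheduled at the end of the SLM-only run-in, so an inert SLM gives no systematic rise, and both links would be positive in at most about 5% of trials (Step 4).

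A reader might also infer that the visit 3 change is independent of SLM. It is not. SLM continues through visit 3, so the two drugs are confounded.

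Nor is it established that axitinib alone must produce the fall. The 44.2% comes from cytokine-refractory patients, while this trial enrolls patients after other systemic therapy, which may include axitinib. What can be seen of the cited imaging study is its title and scan settings, not its results.

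Finally, 21.4 is a hypothesis without a test or threshold. Dual-energy CT is not among the listed objectives, section 14.4 calls the study hypothesis generating, and section 14.3.2 already reports efficacy for the combination.

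All of this stands, and it limits the point to the second link. It does not rescue that link: a visit 2 rise shows that SLM changed iodine uptake, not that the change improved the response to axitinib.

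**Conclusion.** The concern holds for the second link only. A fall in iodine and size at visit 3 describes SLM plus axitinib; it cannot show that SLM made axitinib more effective. The error occurs when SLM raises visit 2 iodine without adding benefit, because the chain would then be reported as supported.

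The logic rests on documented facts: all patients are on both drugs at visit 3, there is no axitinib-only group or benchmark, and axitinib is active. The 21–100% range in Step 3 illustrates the visit 3 link alone. It depends on an assumed axitinib-alone effect, an assumed total SD of log change of 0.36 to 0.54, and a test that the plan does not specify. It is not the false-positive rate of the full hypothesis. The consequence is for interpretation of an exploratory imaging analysis, not for the primary objectives.

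**What to change.** Revise section 21.4 before the dual-energy CT data are analysed:

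1. Base the SLM-specific imaging claim on the visit 1 to visit 2 change in iodine density only. The visit window runs two days past day 14, so confirm that each visit 2 scan preceded the first axitinib dose.
2. Report the visit 3 changes in iodine and size as effects of the combination, not as evidence that SLM made treatment more effective.
3. Examine the link by the association between each patient's visit 1 to visit 2 iodine change and the percentage change in target-lesion sum from baseline to visit 3. Label it exploratory and correlational: vascular biology could drive both changes. Do not use the visit 2 to visit 3 iodine change as the outcome (Step 6).

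The size outcome compares baseline with visit 3, as RECIST assessment under section 12 already requires. No day 14 lesion measurement is needed, which matters because sections 21.1 and 21.5 leave it unclear whether that scan is formally read. No scans or patients are added. The cost is a weaker claim with limited power: about 71–88% for a correlation of 0.5 with 19 to 29 patients scanned, and about 50–60% with 12 to 15.
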